1.2. Study Schema

1.3. Schedule of Events

Study Procedure	Screening Period		Ope	n-Label Ti	reatment]	Period ^a		Follow-u	ıp Period ^b
Visit Days Window	-30 to -1	Day 1	Day 8 (±3 days)	Day 15 (±3 days)	Day 29 (±3 days)	Day 43 (±3 days)	Day 56/ET (±3 days)	Day 70 (±3 days)	Day 112 (±3 days)
Informed consent	X								
Demographics	X								
Medical history	X								
Full physical examination	X						X		
Body weight/height/BMI d	X	X							
Vitals ^e	X	X	X				X		
12-lead ECG		X	X				X		
Safety laboratory tests ^f	X	X	X				X	X	
Urine drug and alcohol breath test screen ^g	X	X							
Urine pregnancy test h	X	X							
Hepatitis and HIV serology	X								
Sparse PK blood sampling i		X	X	X	X	X	X		
Exploratory biomarker sampling j		X	X				X		
Genetic sampling k		X							
Ophthalmic exam and LOCS III 1	X						X	X	X
SCID-5-CT diagnostic interview	X								
MADRS	X	X	X	X	X	X	X	X	
HAM-A	X	X	X	X	X	X	X	X	
CGI-S	X	X	X	X	X	X	X	X	
C-SSRS ^m	X	X	X	X	X	X	X	X	
HAMD-6 ⁿ		4							
GAD-7 ⁿ		•							

Study Procedure	Screening Period	Open-Label Treatment Period ^a						Follow-up Period ^b	
Visit Days Window	-30 to -1	Day 1	Day 8 (±3 days)	Day 15 (±3 days)	Day 29 (±3 days)	Day 43 (±3 days)	Day 56/ET (±3 days)	Day 70 (±3 days)	Day 112 (±3 days)
SF-36 ⁿ		4					-		
EMAW Orienting Questions ⁿ		4					•		
CTQ	X								
CGI-I			X	X	X	X	X	X	
PGI-I			X	X	X	X	X	X	
SAFER Interview (central rater) °	X								
Inclusion/Exclusion Criteria Review	X	X							
12-hour urine collection for cortisol instructions ^p	X						X		
Plasma and saliva cortisol sample collection	X						X		
Wearable monitoring instructions and Mobile application training		X							
Continuous Wearable monitoring q		4					•		
Site download of Wearable data			X	X	X	X	X		
ANC-501 dosing r		•					•		
ANC-501 Dosing Diary dispensed and reviewed by site		-					-		
Dispense study medication		X	X	X	X	X			
Adverse Events s	X	←							→
Prior/ConcomitantMedications t	X	←							—

Abbreviations: AE = Adverse Event; BMI = body mass index; CGI-I = Clinical Global Impression-Improvement; CGI-S = Clinical Global Impression-Severity; C-SSRS = Columbia-Suicide Severity Rating Scale; CTQ = Childhood Trauma Questionnaire, 28-item; ECG = electrocardiogram; ET = early termination; HAM-A = Hamilton Anxiety Rating Scale; HIV = human immunodeficiencyvirus; LOCS III= Lens Opacities Classification System III; MADRS = Montgomery-Åsberg Depression Rating Scale; MDD = major depressive disorder; MGH ATRQ = Massachusetts General Hospital Antidepressant Treatment Response Questionnaire; PGI-I = Patient Global Impression of Improvement; PK = pharmacokinetic; SAE = serious adverse event; SAFER = State vs trait, Assessability, Face and Ecological validity, Rule of 3Ps (pervasive, persistent, and pathological); SCID-5-CT = Structured Clinical Interview for DSM-5 - Clinical Trials Version; HAMD-6= Hamilton Depression Rating Scale (6-item); GAD-7= General

Study Procedure		Screening Period	Open-Label Treatment Period ^a				Follow-up Period ^b			
	Visit Days Window	-30 to -1	Day 1	Day 8 (±3 days)	Day 15 (±3 days)	Day 29 (±3 days)	Day 43 (±3 days)	Day 56/ET (±3 days)	Day 70 (±3 days)	Day 112 (±3 days)

Anxiety Disorder (7-item); SF-36 = Short Form-Health Survey (36-item).

Schedule of Events (continued)

Refer to Section 8 for additional details regarding assessments/procedures.

- a. Subjects who discontinue study treatment before completing the study and those who prematurely withdraw from the study for any reason should undergo Day 56 visit procedures in-clinic as soon as possible and schedule the Day 70 safety assessments (at +2 weeks post ET visit) and Day 112 follow-up ophthalmic visit (at +8 weeks post ET visit).
- b. Subjects will return to the site on Day 70 and 112 for a follow-up visit.
- c. Day 1 procedures are to be completed prior to dosing, except for sparse PK sampling which will be performed prior to dosing and between 0.75 and 2 hours post-dose.
- d. Body weight and height will be measured at screening and BMI will be calculated. Only body weight and BMI calculation will be performed at subsequent visits.
- e. Vital signs include oral temperature (°C), respiratory rate, heart rate, and blood pressure (supine and standing).
- f. Safety laboratory tests will include hematology, serum chemistry, coagulation, and urinalysis. Refer to Table 4 for details.
- g. Urine toxicology for selected drugs of abuse (barbiturates, amphetamines, cocaine, opioids,) and breath test for alcohol.
- h. Urine pregnancy test will be conducted only in female subjects of childbearing potential. Female subjects who prematurely discontinue will have a pregnancy test performed at the ET visit.
- i. A blood sample for sparce PK sampling will be collected pre-dose and between 0.75 and 2 hours post-dose at the Day 1 visit and between 0.75 and 2 hours post-dose, whenever possible, at other indicated visits (with the date and time of the previous dose provided by the subject).
- j. A blood sample for exploratory biomarker analysis will be collected in conjunction with PK sampling on Days 1 (pre- post-dose), 8, and 56.
- k. A genetic sample (blood) for exploratory biomarker testing will be collected before the first dose of drug.
- Ophthalmic exam, including slit-lamp imaging, may be performed by an appropriately trained and qualified individual as delegated by the PI and documented in the Study Delegation Log. However, a licensed ophthalmologist or optometrist must oversee this work and will make the determination on subject eligibility as per inclusion criteria #4. Slit lamp imaging of the lens of both eyes will be taken and sent to a central reader for assessment using the LOCS III. Ideally the exam would be performed after cortisol results are known and the subject is otherwise deemed eligible to continue with screening assessments. Additional slit lamp imaging of the lens of both eyes may be performed during the treatment period and sent to a central reader for assessment using the LOCS III, per Investigator's discretion.
- m. The "Baseline/Screening" C-SSRS form will be completed during screening. The "Since Last Visit" C-SSRS form will be completed at any time of day at all subsequent time points.

03 March 2023 Version 6.0 Confidential Page 26 of 63

- n. The Short Form-Health Survey (36-item) (SF-36) weekly. The Hamilton Depression Rating Scale (6-item) (HAMD-6) and the General Anxiety Disorder (7-item) (GAD-7) will be completed up to twice a day for a minimum of three days per week (to achieve 6 collections per week). Subjects will answer EMA orienting questions up to three times per day in conjunction with the other assessments being collected via the EMA application on their cell phones or the provided device.
- o. Conducted by central reader after Screening visit, but prior to Day 1 visit. The MADRS, MGH ATRQ and confirmation of MDD will be conducted by central rater for determination of eligibility.
- p. Study site personnel will dispense equipment and train subjects on 12-hour urine collection for measuring cortisol level. At the Day 43 visit, study site personnel will dispense equipment and retrain subjects on the 12-hour urine collection to measure cortisol levels (the collection will be returned to the site at the Day 56 visit). On Day 54, the site will contact the subject to remind them to begin collection on Day 55.
- q. Subjects will wear their wearable watch-like device throughout the day and night except when charging.
- r. At the Day 1 visit, subjects confirmed as eligible will receive a 50 mg dose of study drug at the study site prior to eating. All other doses will be taken by the subjects at home.
- s. All AEs will be recorded from study drug administration on Day 1 until Day 112 visit. Serious adverse events that occur subsequent to the signing of the informed consent (i.e., during the Screening Period) as a result of study participation will be recorded, as well as all SAEs occurring from study drug administration on Day 1 until Day 112 visit.
- t. Includes medications taken within 30 days prior to informed consent and throughout the study.

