At the Day 56 visit, subjects will take their last study medication and visit the site to return their 12-hour urine collection, all remaining medication, the dosing diary, and wearable watches. Study procedures/assessments will be conducted, including an ophthalmic exam and slit lamp imaging of the lenses of both eyes. Images will be sent to a central reader for assessment using the LOCS III. Collection of plasma and saliva cortisol samples will also be conducted.

The same rater should perform the CGI-S, CGI-I, and MADRS assessments throughout the study on a given subject when possible.

Follow-up Period (Day 70 and Day 112)

Subjects will return to the site for a follow-up visit on Day 70 and Day 112. Study procedures/assessments will be conducted, including an ophthalmic exam and slit lamp imaging of the lenses of both eyes. Images will be sent to a central reader for assessment using the LOCS III. Concomitant medications will be reviewed, and Aes recorded.

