7. DISCONTINUATION OF STUDY TREATMENT AND SUBJECT WITHDRAWAL

7.1. Discontinuation of Study Treatment

A subject must be discontinued from study treatment for any of the following:

- 1. Unacceptable toxicity, despite maximal supportive care and/or dose reduction.
- 2. Subjects exhibiting a change in the LOCS III greater than or equal to 0.5 in Nuclear Opalescence, Cortical Opalescence or Posterior Subcapsular Opalescence in either eye or clinically significant eye changes (e.g., incident of cataract).
- 3. Investigator decision (may include the need for antidepressant therapy or other therapy not otherwise permitted in the study, including ECT or changes to cognitive/behavioral psychotherapy) or noncompliance with study requirements.
- 4. Subject becomes or intends to become pregnant.
- 5. Subject withdrawal of consent for further study treatment.
- 6. Study termination by the Sponsor.

Subjects discontinuing treatment should complete the Early Termination visit procedures and enter the Follow-up Period.

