8.3.1. Laboratory Assessments

See Table 4 for the list of clinical laboratory tests to be performed and the Schedule of Events (Section 1.3) for timing and frequency.

Table 4: Laboratory Assessments

Laboratory Test	Parameters
Hematology	Hemoglobin, hematocrit, RBC (including mean corpuscular hemoglobin, mean corpuscular volume, mean corpuscular hemoglobin concentration), WBC with differential (neutrophils [absolute count] and lymphocytes, monocytes, eosinophils, basophils), and platelet count.

Laboratory Test	Parameters
Coagulation	PT, INR, aPTT.
Serum chemistry	Non-fasting: albumin, alanine aminotransferase (ALT), aspartate aminotransferase (AST), alkaline phosphatase, amylase/lipase, bicarbonate, bilirubin (total and direct), BUN (urea where BUN not tested), calcium, chloride, creatinine, glucose, magnesium, phosphorus, potassium, sodium, and total protein. Subjects found to have treatment-emergent laboratory toxicity of Grades 3 or 4 will be monitored at least weekly until resolution.
Urinalysis	pH, protein, ketones, bilirubin, nitrite, blood, leukocytes, specific gravity, urobilinogen. Reflex to microscopic exam when positive for protein, blood, nitrite, or leukocytes.
Pregnancy test	Urine pregnancy test will be conducted in only female subjects of childbearing potential. Female subjects who prematurely discontinue will have a pregnancy test performed at the ET visit.
Serology	HBsAg, HCV Ab, HIV antibody
Urine drug and alcohol screen	Urine toxicology for selected drugs of abuse (barbiturates, amphetamines, cocaine, opioids) and breath test for alcohol.
Plasma, saliva, and 12-hour urine collection for measurement of cortisol level,	Study site personnel will dispense the equipment and train subjects on how to collect a 12-hour urine collection for measuring cortisol level. Saliva collection at screening should be a morning sample.

Abbreviations: ALT = alanine aminotransferase; aPTT = activated partial thromboplastin time; AST = aspartate aminotransferase; BUN = blood urea nitrogen; ET = early termination; HBsAg = hepatitis B surface antigen; HCV Ab = hepatitis C virus antibody; HIV = human immunodeficiency virus; INR = International Normalized Ratio; PT = prothrombin time; RBC = red blood cell; WBC = white blood cell.

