8.4.7. Pregnancy

Details of all pregnancies in female subjects or in female partners of male subjects (after appropriate consent for use of medical information has been obtained) will be reported to the Sponsor or designee at the email noted in Section 8.4.5 within 24 hours of the Investigator's awareness, using a Pregnancy Report form.

While pregnancy itself is not considered to be an AE or SAE, any pregnancy complication or elective termination of a pregnancy for medical reasons will be reported as an AE or SAE. Abnormal pregnancy outcomes (e.g., spontaneous abortion, fetal death, stillbirth, congenital anomalies, ectopic pregnancy) are considered SAEs and will be reported as such.

The subject/pregnant female partner will be followed to determine the outcome of the pregnancy. The Investigator will collect follow-up information on the subject/pregnant female partner and the neonate, and forward to the Sponsor or designee.

Any female subject who becomes pregnant while participating in the study will discontinue study drug.

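### Women who complete treatment have no scheduled pregnancy test after the pre-dose Day 1 test, while early discontinuers are tested at the same Day 56/ET visit

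*Protocol*

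**What the plan says.** In the Protocol 1.3 Schedule of Events, the row "Urine pregnancy test h" is marked at Screening and Day 1 and nowhere else. SAP Table 1 shows the same two marks. Footnote c requires Day 1 procedures, apart from the sparse PK samples, to be finished before dosing. Exclusion criterion 11 uses both results for eligibility.

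Footnote h limits the test to female subjects of childbearing potential and adds: "Female subjects who prematurely discontinue will have a pregnancy test performed at the ET visit". The pregnancy test entry in Table 4 (Protocol 8.3.1) opens with "Urine pregnancy test will be conducted in only female subjects of childbearing potential" and repeats the ET rule. Footnote h of SAP Table 1 does the same.

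The ET visit has no column of its own. It shares the Day 56/ET column, and footnote a says that subjects who stop early "should undergo Day 56 visit procedures in-clinic as soon as possible".

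Pregnancy has consequences elsewhere in the protocol:

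- Section 7.1, item 4, requires study treatment to stop if "Subject becomes or intends to become pregnant".
- Section 8.4.7 requires a report within 24 hours of the Investigator's awareness, and "The subject/pregnant female partner will be followed to determine the outcome of the pregnancy".
- Inclusion criterion 14 requires contraception until 90 days after the last dose.

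**The concern.** Both tests that a completer receives are eligibility tests taken before any exposure. The only test that looks back over exposure is given to women who stopped early and so had less of it. Women with the full 8 weeks get none, and the documents give no reason for the difference.

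The stopping rule and the outcome follow-up work only once someone knows of the pregnancy. For a completer, no scheduled procedure after Day 1 would reveal it. AE questioning is a weak substitute: Section 8.4.4.2 says subjects are not asked about specific events, and Section 8.4.7 says pregnancy itself is not an AE. Contraception lowers the risk but does not detect a failure. At stake is late or missed recognition of a pregnancy exposed to an investigational drug, and with it the required outcome and neonatal follow-up.

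**Working it through.** The plan gives no figure to reproduce here. The check is a reading of the schedules, followed by day counts.

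**Scheduled tests by type of subject** (Protocol 1.3 row and footnotes a, c and h; Table 4; SAP Table 1)

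| | Screening | Day 1, pre-dose | Days 8, 15, 29, 43 | Day 56/ET | Days 70, 112 | Total | After first dose |
|---|---|---|---|---|---|---|---|
| Completer | yes | yes | no | no | no | 2 | 0 |
| Early discontinuer attending ET | yes | yes | no | yes | no | 3 | 1 |

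The visits after Day 1 are Days 8, 15, 29, 43, 56, 70 and 112, which makes 7. A completer is tested at none of them.

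**Could a table mark have been lost in text extraction?** This is unlikely. The protocol and SAP schedules agree. If the Day 56/ET cell were marked, footnote a would already give early discontinuers the test, and the second sentence of footnote h would be unnecessary.

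**Time without a scheduled test, completer** (nominal days, ±3-day visit window)

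- To the end-of-treatment visit: 56 − 1 = 55 days (53 − 1 = 52 to 59 − 1 = 58).
- To the last visit: 112 − 1 = 111 days (109 − 1 = 108 to 115 − 1 = 114).
- The contraception requirement runs to Day 56 + 90 = 146, which is 146 − 112 = 34 days past the last visit.

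**Expected conceptions during dosing.** The formula is women × annual contraceptive failure rate × 56/365. Neither of the first two inputs is in the documents. I assume 5 to 15 women of childbearing potential among the up to 20 enrolled, and a failure rate of 1% to 15% a year.

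- Low: 5 × 0.01 × 56/365 = 0.008
- Middle: 10 × 0.08 × 56/365 = 0.12
- High: 15 × 0.15 × 56/365 = 0.345

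**What a later test could achieve**

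- Day 56: Protocol 4.1 states "At the Day 56 visit, subjects will take their last study medication". A test that day cannot shorten exposure, so it serves detection and follow-up only.
- Day 29: doses on Days 30 to 56 remain, which is 27 of 56. With both windows the number runs from 21 (visit on Day 32, last dose Day 53: Days 33 to 53) to 33 (visit on Day 26, last dose Day 59: Days 27 to 59).

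**The case against.** The strongest reply is that this is a choice and not an error. The schedule, the footnote, Table 4 and the SAP agree with one another, and no requirement in the documents is breached. Several controls already exist: two negative tests before dosing, contraception to 90 days after the last dose, mandatory stopping, 24-hour reporting, and AE recording to Day 112. An unscheduled test is not forbidden. Even the high case above is well under one event, and it needs 15 of at most 20 subjects to be women of childbearing potential, all at the top failure rate. That argues for modest weight, and I accept it. It does not explain why the women with the longest exposure are the ones left untested.

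Three further points stand as limits:

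- A urine test on Day 56 would miss very recent conceptions. If a test turns positive about two weeks after conception (an assumption), those in the last 14 of 56 days, a quarter of dosing, escape it. The existing ET test shares this limit.
- An early discontinuer has a third test only if the ET visit takes place. Subjects who are lost to follow-up, or who withdraw consent to further assessments, may have none after Day 1 either.
- A changed schedule is a protocol amendment. It needs IRB approval before implementation (Protocol 11.3), and subjects must be re-consented to the most current consent form (11.2). Section 4 of the SAP already reports two discontinued subjects, so the study was under way when that version was written, and the change may come too late for some or all participants.

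**Conclusion.** The concern holds. Followed as written, the plan leaves every woman of childbearing potential who completes treatment without a pregnancy test at any of the 7 visits after Day 1, including the visit at which an early discontinuer is tested. The scheduled gap is 55 days to the end of treatment and 111 days to the last visit.

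This is a gap in safety scheduling, worth closing because the event matters and the test is simple. Few events are expected: about 0.01 to 0.35 conceptions during dosing, a range that rests entirely on the assumed numbers of women and failure rates. The counts of tests and days rest on the documents alone. No efficacy result or other statistical figure in the plan changes.

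**What to change.** Mark the urine pregnancy test at Day 56/ET in the Schedule of Events. Reword footnote h and the Table 4 entry so that every female subject of childbearing potential is tested at Screening, Day 1 and Day 56/ET, and align SAP Table 1 and its footnote h. Protocol 8.4.7 needs no change.

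If item 4 of Section 7.1 is meant to act on a scheduled test, add a dipstick at an existing dispensing visit such as Day 29, when 27 doses remain. If conceptions late in dosing are a concern, Day 70 is another option, since safety laboratory tests are scheduled there. Neither addition is needed for the main change to be worthwhile.

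The cost is one table mark, one reworded sentence in footnote h and in Table 4, the matching SAP edit, and one dipstick per eligible woman. Urine is already collected at Day 56: footnote f states "Safety laboratory tests will include hematology, serum chemistry, coagulation, and urinalysis", and that row is marked there. A Day 29 test would need an extra urine specimen, because no safety laboratory tests are scheduled at that visit. The administrative cost is the amendment itself, with IRB approval and re-consent, so it is best combined with another amendment or carried into the next protocol if enrolment has closed.

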2.3.1. Evaluation in Humans

Three Phase 1 studies (a single ascending dose [SAD] study [TS121-US101], a multiple ascending dose [MAD] study [TS121-US102], and a PET receptor occupancy study [TS121-US103]) and one Phase 2 study (TS121-US201) have been conducted in the United States.

Pharmacokinetic (PK) studies indicate that following single and multiple oral administration of ANC-501, increases in plasma ANC-501 peak and total exposures (maximum plasma concentration [C_{max}] and area under the concentration-time curves [AUCs]) were observed with increases in dose. ANC-501 reached C_{max} within 4 hours after dosing and declined with apparent half-life ($t_{1/2}$) of approximately 20 hours. No food effect was observed on AUCs of ANC-501, while C_{max} was reduced under fed conditions. In the MAD study, the plasma trough concentrations of ANC-501 appeared to reach steady state by 5 days after dosing and the exposures accumulated to approximately 2 times. Low renal clearance (CL_r) suggested minimal contribution of the urinary excretion of ANC-501. Though two metabolites (M5 and M9) were found in plasma, the unchanged form was proposed as a predominant component. In addition, PET study revealed the relationship between plasma exposure of ANC-501 and V_{1b} receptor occupancy in the pituitary.

Overall, 78 healthy and 32 adult subjects with MDD were administered ANC-501 to date. In the Phase 2 study, there was no statistically significant difference observed in the primary endpoint (Montgomery-Åsberg Depression Rating Scale [MADRS] Change from Baseline to Week 6positive trends were observed for the scores of depression scales in ANC-501 treated groups (10 mg and 50 mg) versus placebo. The lack of statistical significance may be attributable to the small number of subjects enrolled.

Safety Findings in Clinical Studies

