4. STUDY DESIGN

4.1. Overall Design

This is a single-arm, open-label Phase 2 study to assess the safety, tolerability, pharmacokinetics (PK), and efficacy of ANC-501 oral capsules as adjunctive treatment in subjects diagnosed with major depressive disorder (MDD).

With the exception of subjects permitted to use current stable antidepressant treatment, initiation of psychotropic medications and other medications that may potentially have an impact on efficacy or safety endpoints will not be allowed between screening and completion of the Day 56 assessments. Psychotropic medications, which must have been initiated at least 8 weeks prior to screening, must remain at a stable dose until completion of the Day 56 assessments. During the study, efficacy and safety assessments will be performed and blood samples collected for PK analysis of ANC-501 and future exploratory biomarker and genetic analysis. A wearable watch-like device will collect data on biometrics, which may be used for exploratory analyses.

Subjects will receive 50 mg ANC-501 Capsules (5×10 mg capsules) orally once daily at least 1 hour prior to the morning meal for 8 weeks beginning with the first dose administered in the clinic on Day 1, and will return to the clinic for scheduled visits on Days 8, 15, 29, 43, and 56. Follow-up visits will occur on Day 70 and 112. All visits after Day 1 allow a visit window of ± 3 days.

Total duration of participation is 20 weeks (up to 30 days screening, 8 weeks dosing, 8 weeks follow-up).

The following is an overview of study procedures/assessments (refer to the Schedule of Events [Section 1.3] for specific procedures/assessments and their timing, with further details located in Section 8):

Screening Period (Day -30 to Day -1)

After providing informed consent, eligibility assessments will include review of demographics, medical history, prior/concomitant medications, full physical examination, vital sign assessments, body weight/height/body mass index (BMI) measurements, urine pregnancy test (for female subjects of childbearing potential), urine drug and alcohol breath test screen, safety laboratory tests (i.e., hematology, serum chemistry, coagulation, and urinalysis), hepatitis and human immunodeficiency virus (HIV) screen, and plasma and saliva cortisol sample collection.

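### The end-of-treatment urine cortisol collection is fixed to Day 55, although the visit at which the urine is returned and dosing ends may fall on Days 53 to 59

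*Protocol*

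**What the plan says.** - **Visit window.** Protocol 4.1 states "All visits after Day 1 allow a visit window of" ±3 days, and the column header in the Schedule of Events reads "Day 56/ET (±3 days". The SAP schedule carries the same window.
- **What happens at that visit.** Protocol 4.1: "At the Day 56 visit, subjects will take their last study medication and visit the site to return their 12-hour urine collection". Subjects also hand back "all remaining medication, the dosing diary, and wearable watches", so there is no dosing afterwards.
- **When the urine is collected.** Footnote p: "On Day 54, the site will contact the subject to remind them to begin collection on Day 55". Of the same sample it says "the collection will be returned to the site at the Day 56 visit". Protocol 1.1 and 4.1 and footnote p of the SAP schedule repeat the two fixed days. None of them gives those days a window or ties them to the date on which the visit is booked.
- **The schedule row.** "12-hour urine collection for cortisol instructions" is marked at Screening and at Day 56/ET, with no mark at Day 43. Footnote p, attached to that row, has the equipment dispensed and the subject retrained at Day 43.
- **Early termination.** Footnote a sends subjects who stop early to the Day 56 procedures as soon as possible. It does not say what happens to the urine collection if they stop before the Day 43 kit is issued.
- **Analysis.** SAP 9.4.1 places cortisol sampling at screening and Day 56 and summarises observed values and change from baseline. It has no rule on collection date or on treatment status at collection. SAP 5.1 excludes imputation for values of this kind.

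**The concern.** The visit can move by three days in either direction, but the reminder and the collection cannot. For the earlier permitted visit days the sequence runs backwards: dosing ends and the return visit takes place before the collection has begun. The sample is then either not obtained or is collected after the last dose, with no visit before Day 70 at which to hand it in.

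Urine cortisol is the marker used for entry (inclusion criterion 12) and features in the case for the dose (Protocol 4.2). The plan schedules one post-baseline urine measurement. With at most 20 subjects and no imputation, a few missing values would thin the summary. A few values taken after the last dose could enter it under the Day 56 label with nothing to mark them.

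**Working it through.** No figure in the plan needs reproducing here; the check is day arithmetic.

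**Inputs**
- Visit window: 56 − 3 = 53 to 56 + 3 = 59, which is 7 permitted days (Protocol 1.3, 4.1).
- Collection starts on Day 55; reminder on Day 54 (footnote p).
- Last dose on the day of the visit (Protocol 4.1).
- Half-life "of approximately 20 hours" (Protocol 2.3.1).
- Up to 20 subjects (Protocol 9.2).

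**Step 1: collection day minus visit day**

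| Visit on Day | 55 − visit day | Literal result |
|---|---|---|
| 53 | +2 | Reminder and collection both follow the visit and last dose |
| 54 | +1 | Collection follows the visit and last dose |
| 55 | 0 | Same day; probably incomplete at the visit |
| 56 | −1 | Collected before the visit, on treatment |
| 57 | −2 | Collected before the visit, on treatment |
| 58 | −3 | Collected before the visit, on treatment |
| 59 | −4 | Collected before the visit, on treatment |

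The Day 55 row is an inference. Doses are taken every morning, and the PK sample is wanted 0.75 to 2 hours after the dose where possible, which points to a morning visit. No clock time is given for the visit or for the collection.

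**Step 2: share of permitted days**
- Days 53 and 54: 2/7 = 29%.
- Days 53 to 55: 3/7 = 43%.

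**Step 3: subjects, under assumed visit patterns** (the documents give none)
- All visits on Day 56 or later, or sites counting back from the booking: 0 of 20.
- Weights 1-2-3-4-3-2-1 over Days 53 to 59 (sum 16): 3/16 × 20 = 3.75 to 6/16 × 20 = 7.5, about 4 to 8 of 20.
- Even spread: 2/7 × 20 = 5.7 to 3/7 × 20 = 8.6, about 6 to 9 of 20.

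Twenty is the enrolment ceiling; anyone who stops early reduces the base.

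**Step 4: drug remaining at a late collection**, as 0.5^(hours/20), assuming first-order decline
- 24 h: 0.5^1.2 = 0.44
- 48 h: 0.5^2.4 = 0.19
- 72 h: 0.5^3.6 = 0.08

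Depending on the hour at which collection starts, a Day 54 visit corresponds to about 24 to 48 h after the last dose and a Day 53 visit to about 48 to 72 h.

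**Step 5: effect of counting back.** With collection on visit day − 1, the start falls on Days 52 to 58 for visits on Days 53 to 59. It precedes the visit and the last dose on 7 of 7 permitted days, against 4 of 7 as written.

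**The case against.** The strongest reply is that Days 54, 55 and 56 are one nominal sequence: remind, collect, return. A sensible site whose visit is booked for Day 53 would count back from it and would not telephone the day after the visit to start a collection. This stands as a reason why the loss may be small or nil. It does not remove the conflict, because the documents nowhere say that the days are nominal. Elsewhere, for follow-up after early termination, the protocol does state timing relative to a visit.

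Several stronger readings are tempting and are not supported:

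- **That early visits necessarily lose the sample, or that 29 to 43% of subjects will.** Those are shares of permitted days. They become shares of subjects only under an assumed even spread.
- **That late samples are drug-free.** They are taken after the last dose, but by the stated half-life roughly 44% remains at 24 h and 19% at 48 h.
- **That the table would lead sites to issue the kit at the final visit.** The row carries footnote p, and Protocol 1.1 and 4.1 repeat the Day 43 dispensing. The missing mark is a matter of alignment.
- **That selection, the main efficacy result or all post-baseline cortisol data are compromised.** Entry uses the screening sample, the primary efficacy endpoint is MADRS, and plasma and saliva cortisol are taken at the Day 56 visit itself.

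**Conclusion.** The point holds as a conflict between a fixed collection day and a movable visit. Under the literal text, 2 of the 7 permitted visit days certainly fail. A third, Day 55, probably fails, on the inference of a morning visit. The consequence is a missing urine sample or one collected one to two days after the last dose.

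How many subjects this affects cannot be determined from the documents. The range runs from 0 to about 6 to 9 of 20, the upper end resting on an even spread of visits. The damage is confined to the exploratory urine cortisol endpoint, which is summarised descriptively. It is worth correcting because the plan as written offers no way to tell an on-treatment value from a later one.

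**What to change.** 1. In footnote p, Protocol 1.1 and 4.1, and the SAP schedule, replace the fixed days with: remind the subject 2 days before, and collect on the day before, the scheduled Day 56 visit.
2. Align the schedule row with its footnote: equipment and retraining at Day 43, return at Day 56.
3. State that urine cortisol is not required at early termination if no kit has been dispensed. Supplying a kit at that point could need an extra contact, and in someone who has already stopped treatment it would give a sample taken after the last dose.
4. In SAP 9.4.1, flag urine samples collected after the last dose, and summarise the change from baseline with and without them. This needs the collection date to be recorded alongside the last-dose date.

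The SAP already refers to subjects who have been discontinued, so the study is under way. Schedule wording cannot repair samples already taken; item 4 still helps with those, and with visits moved at short notice. The cost is minor wording changes and one extra summary, with no added visit or procedure.
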